13 PROTOCOL ADHERENCE AND INVESTIGATOR AGREEMENT

Before the start of the study, the study protocol and/or other relevant documents will be approved by the IRB or competent authority, in accordance with local legal requirements.

The sponsor must ensure that all ethical and legal requirements have been met before the first subject is enrolled in the study.

This protocol is to be followed exactly. To alter the protocol, amendments must be written, receive approval from the appropriate personnel, and receive IRB approval prior to implementation (if appropriate). Following approval, the protocol amendment(s) will be submitted to the Investigational New Drug application under which the study is being conducted.

Administrative changes (not affecting the subject benefit/risk ratio) may be made without the need for a formal amendment. All amendments will be distributed to all protocol recipients, with appropriate instructions.

14 PROCEDURE FOR COMPLETION AND CORRECTION OF THE CASE REPORT FORM

This study will use electronic data collection. Data obtained during this study should be entered in the eCRFs or collected by electronic subject diary promptly and correctly. All data entered into the eCRF should be accurate and attributable to the subject's source documents. Measurements for which source documents are usually available include laboratory assessments, MRIs, and X-rays. Some patient-reported outcomes will be completed on electronic devices by subjects and be stored in a database. These entries should not be changed by anyone except by the individual subject.

Data from external sources, such as laboratory data, MRIs, and X-rays, will be processed outside the clinical database according to the study data management plan.

15 DIRECT ACCESS TO SOURCE DATA

During the study, blinded and unblinded monitors will make site visits to review protocol compliance, compare eCRF entries and individual subject medical records, assess product accountability, and ensure that the study is being conducted according to pertinent regulatory requirements as applicable to their study role specified in the clinical monitoring plan. Entries in the eCRF will be verified with source documentation. The review of medical records will be performed in a manner to ensure that subject confidentiality is maintained and the study blind is protected.

Checking of the eCRF entries and other study electronic systems for completeness and clarity and cross-checking with source documents will be required to monitor the progress of the study. Moreover, regulatory authorities of certain countries, IRBs, and/or the sponsor may wish to carry out such source data checks and/or on-site audit inspections. Direct access to

source data will be required for these inspections and audits; they will be carried out giving due consideration to data protection and medical confidentiality. The investigator assures the sponsor or designee of the necessary support at all times.

16 DATA QUALITY ASSURANCE

The sponsor or designee will conduct a site visit to verify the qualifications of each investigator, inspect the site facilities, and inform the investigator of the responsibilities and procedures for ensuring adequate and correct documentation.

The investigator is required to prepare and maintain adequate and accurate case histories designed to record all observations and other data pertinent to the study for each study participant. All information recorded in the eCRF for this study must be consistent with the subjects' source documentation (e.g., medical records).

17 ARCHIVING OF SOURCE DATA AND OTHER RECORDS

According to ICH guidelines, essential documents should be retained for a minimum of 2 years after the last approval of a marketing application in an ICH region and until there are no pending or contemplated marketing applications in an ICH region or at least 2 years have elapsed since the formal discontinuation of clinical development of the investigational product. However, these documents should be retained for a longer period if required by the applicable legal requirements.

18 LIABILITY AND INSURANCE

The sponsor will take out reasonable third-party liability insurance cover in accordance with all local legal requirements. The civil liability of the Investigator, the persons instructed by him or her and the hospital, practice, or institute in which they are employed and the liability of the sponsor with respect to financial loss due to personal injury and other damage that may arise as a result of the carrying out of this study are governed by the applicable law.

The sponsor will arrange for subjects participating in this study to be insured against financial loss due to personal injury caused by the pharmaceutical products being tested or by medical steps taken in the course of the study.

19 PUBLICATION POLICY

By signing the study protocol, the investigator agrees with the use of results of the study for the purposes of national and international registration, publication, and information for medical and pharmaceutical professionals. If necessary, regulatory authorities will be notified of the investigator's name, address, qualifications, and extent of involvement.

An investigator shall not publish any data (e.g., poster, abstract, or paper) without having consulted with the sponsor in advance and having received written authorization.

PGIC	Patient Global Impression of Change
PP	Per-protocol
PT	Preferred Term
QOL	Quality of Life
SD	Standard Deviation
SLR	Straight Leg Raise
SF-36	36-item Short Form Health Survey
SOC	System Organ Class
TEAE	Treatment-emergent Adverse Event
U	Units

VAS	Visual Analogue Scale
WPAI	Work Productivity and Activity Impairment Questionnaire

1. PURPOSE OF THE ANALYSES

The purpose of the analyses described in this document is to compare the safety and efficacy of a single intervertebral disc injection of SI-6603 to a sham injection in subjects with lumbar disc herniation (LDH).

2. PROTOCOL SUMMARY

2.1 Study Objectives

The primary objective is to evaluate the efficacy of a single-dose intervertebral disc injection of SI-6603 at a dose of 1.25 units (U) compared to control in subjects with LDH by comparing the change in worst leg pain during the past 24 hours, as assessed by visual analogue scale (VAS), from baseline to Week 13 after injection of the investigational product.

The secondary objectives are to evaluate the efficacy of SI-6603 1.25 U for key secondary endpoints, and to demonstrate whether SI-6603 1.25 U is safe and well tolerated.

Key secondary endpoints include:

- Change from baseline to Week 13 in herniation volume
- Change from baseline to Week 13 in Oswestry Disability Index (ODI) score
- Change from baseline to Week 52 in average worst leg pain score during the past 24 hours over the previous 7 days, as assessed by 100 mm VAS.

Supportive endpoints may be found in section [7.2](#).

2.2 Overall Study Design and Plan

Up to three weeks following the screening, subjects will be randomized and injected at Week 0. Subjects will receive a single injection of SI-6603 or a sham injection and will be followed for 52 weeks for the efficacy and safety evaluations found in the schedule of events. Subjects will return for follow-up visits at Weeks 1, 2, 4, 6, 13, 26, 39 and 52.

2.3 Study Population

Subjects will meet the following key criteria:

- Ages 30 to 70 (inclusive)
- Have contained posterolateral LDH at either L4-L5 or L5-S1 (or L5-L6):
 - with the presence of demonstrable nerve root impingement, as assessed by Magnetic Resonance Imaging (MRI);
 - chief complaint of unilateral radiculopathy and/or radicular leg pain corresponding to the ipsilateral leg and distribution of the affected nerve root; and
 - positive result of Straight Leg Raise (SLR) test ($\leq 70^\circ$) only on the ipsilateral leg having chief complaint of radiculopathy corresponding to the pain and distribution of the affected nerve root.
- Symptoms of radiculopathy and/or radicular leg pain only in the unilateral leg corresponding to the distribution of the affected nerve root for 6 weeks or more but 1 year or less, and which is still ongoing at the time of informed consent.

- Subjects whose worst leg pain (100 mm VAS) for the 7 consecutive days up to the day before randomization meets following conditions:
 - at least 5 worst leg pain scores on the days when not using any rescue medications or increasing or adding non-prohibited concomitant medications to treat LDH;
 - the mean of the worst leg pain scores is 50 to 90 mm; and
 - the range of fluctuation in worst leg pain scores over the 7 days (difference between minimum and maximum scores) is ≤ 25 mm.
- $\geq 30\%$ on the ODI at the time of randomization

The full inclusion and exclusion criteria may be found in the protocol.

2.4 Treatment Regimens

Subjects will be randomized to receive a single dose injection of SI-6603 1.25 U into an intervertebral disc or a sham injection.

2.5 Randomization

All eligible subjects will be randomized on a 1:1 basis to SI-6603 or control based on a computer-generated randomization schedule. The randomization will be balanced by randomly permuted blocks and stratified by site.

2.6 Sample Size Determination

It is planned to enroll approximately 320 subjects, 160 in the SI-6603 group and 160 in the control group.

Sample size estimation is based on using the mean difference in the worst leg pain score change from baseline in the primary efficacy analysis. The following assumptions were made to compute the sample size:

- The 2-sample t-test comparing the group means of the change from baseline was used. (The 2-sample t-test approximates the test of the null hypothesis based on the repeated measures model that will be used in the primary efficacy analysis.)
- Treatment difference between SI-6603 and control groups of 12 mm
- Common standard deviation (SD) of 30 mm
- Dropout rate of 15%
- Power of 90%
- Two-sided significance level of 5%

3. GENERAL ANALYSIS AND REPORTING CONVENTIONS

All efficacy analyses will use a two-sided alpha = 0.05 test unless otherwise stated. P-values will be rounded to four decimal places. If a p-value is less than 0.0001, it will be reported as “<0.0001.”

Continuous data will be described using descriptive statistics: sample size, mean, SD, median, Q1 and Q3, minimum, and maximum. Minimums and maximums will be reported with the same precision as the raw values; medians, Q1, Q3 and means will show precision to one decimal place greater than the raw values; SDs will show precision to two decimal places greater than the raw values. For example, if height is recorded in whole centimeters, min and max will be displayed as whole centimeters, means will be shown as xxx.x and SD will be shown as xxx.xx. Data will be displayed in all listings sorted by treatment group and subject identification number. Subjects will be identified in the listings by the subject identification number concatenated with the investigator number.

When count data are presented, the percentage will be suppressed when the count is zero in order to draw attention to the non-zero counts. The denominator for all percentages will be the number of subjects with non-missing data in that treatment group within the population of interest.

For the duration of leg pain covariate, if partial dates are provided, then missing dates will be imputed as the 15th for a missing day and July for a missing month, consistent with prior protocols.

3.1 Baseline values

For visit-based measures, baseline will be the last non-missing value prior to injection. For diary-based measures, the baseline will be the average of the scores for the 7 consecutive days up to the day prior to randomization (independently for worst leg pain and worst back pain). Per the inclusion criteria, subjects should have a minimum of 5 non-missing values; however, if a subject is inadvertently randomized with fewer values, then the baseline will be the mean of the available values from that 7 day period. Note that post-baseline visits were scheduled per the protocol with the injection date as day 1; in rare instances, this may be after the randomization date. In these cases, the baseline will be anchored around the randomization visit. Additionally, in the instance that a subject is inadvertently entered into the randomization system and assigned a kit on a day other than their visit 2A, the anchor date will be the day that they were confirmed to have qualified for the trial (typically the day of visit 2A).

4. ANALYSIS POPULATIONS

Three analysis populations as described below will be utilized in reporting the study results. All efficacy analyses will be performed on the modified intention-to-treat (mITT) population, with some analyses repeated on the per-protocol (PP) population.

All safety analyses will be performed on the safety population.

4.1 Modified Intention-to-Treat

The mITT population is defined as all randomized subjects who received the study injection, analyzed according to the assigned treatment.

4.2 Per-Protocol

The PP population is defined as all mITT subjects who had no major protocol deviations that could affect the primary efficacy assessment. The details of major protocol deviations are described in section [5.2](#), and included subjects will be determined prior to unblinding.

4.3 Safety

The safety population is defined as all randomized subjects who received the study injection, analyzed according to the treatments subjects received.

5. STUDY SUBJECTS

5.1 Disposition of Subjects

A disposition table of subjects will include the number and percentage of subjects for the following categories: subjects screened, subjects randomized, subjects treated (safety sample), subjects in the mITT sample, subjects in the PP sample, subjects completing through Week 13, subjects completed study, and subjects discontinued from the study. A separate summary of discontinuations through Week 13 will also be presented. All percentages will be based on the number of subjects randomized (with the exception of subjects screened). Additionally, the number of subjects excluded from each population and reason for exclusion will be presented overall and by site.

The reasons for study discontinuation will also be summarized in this table. The reason for discontinuation may include any of the following: lack of efficacy, death, adverse event, lost to follow-up, failure to meet randomization criteria, protocol violation, physician decision, withdrawal by subject, pregnancy, study terminated by sponsor, and other. Subjects that do not complete the study will be flagged if they had early termination due to confirmed COVID-19, early termination at site discretion due to COVID-19, or early termination at subject discretion due to COVID-19; this will be summarized with the number and percentage of subjects in each category. Only the primary reason for study discontinuation will be recorded for a given subject.

The number and percentage of subjects attending each visit will be summarized. Due to the COVID-19 pandemic, visits could be in-person, remote or a combination; the reason for a remote visit could be due to the subject having confirmed COVID-19, at site discretion due to COVID-19, at subject discretion due to COVID-19 or other reasons. Likewise visits may have been missed or canceled due to the subject having confirmed COVID-19, at site discretion due to COVID-19, at subject discretion due to COVID-19 or other reasons. Additionally, individual assessments may have been omitted due to COVID-19; this is recorded on the CRF.

The type of visit (in-person, remote, or combination), the reason for remote visits, the reason visits were missed and assessments missed due to COVID-19 will be summarized with counts and percentages for each visit and treatment group.

A listing will present data concerning subject disposition and other reasons for discontinuation. Additionally, a listing will show the visit attendance, type of visit, reason for remote/missed visit, and assessments missed due to COVID-19 for each subject.

5.2 Protocol Deviations

Protocol deviations will be categorized as major or minor prior to database lock and unblinding according to Protocol Deviation Plan. Additionally, deviations are categorized whether they are related to the COVID-19 pandemic. All recorded protocol deviations and their categorization will be presented in a listing.

6. DEMOGRAPHICS, BASELINE CHARACTERISTICS, CONCOMITANT MEDICATIONS, MEDICAL HISTORY

6.1 Demographics and Other Baseline Characteristics

Demographics and baseline characteristics will be summarized by treatment for the mITT, safety, and PP populations. With the exception of the worst leg pain scores, Week 0 will be presented unless an outcome is not collected, in which case the screening visit will be used. For VAS pain scores, the baseline will be the average of the 7 daily worst pain leading up to the randomization visit. Outcomes presented will include:

- age
- sex
- race
- ethnicity
- height
- baseline weight
- body mass index (BMI)
- smoking history
- occupation
- days since diagnosis
- herniation site
- location of herniation
- location of radicular leg pain
- days since onset of current radicular leg pain
- ongoing low back pain caused by herniation
- VAS pain score for worst leg pain
- VAS pain score for worst back pain
- ODI score

All outcomes except the VAS pain scores and ODI scores will appear in a listing of baseline characteristics; VAS pain scores and ODI scores will appear with all other visits in the efficacy listings.

Note that 36-item Short Form Health Survey (SF-36), EQ-5D-5L, and Work Productivity and Activity Impairment Questionnaire (WPAI) assessments are collected at baseline; however, baseline values of these will be presented only on their associated displays.

6.2 Prior and Concomitant Medications/Therapies

Concomitant medications/therapies include all medications taken at any point following the injection of the study therapy; in case of partial dates, a medication will be considered to be concomitant unless the partial dates clearly exclude the post-injection period.

Concomitant medications will be coded using the WHO Drug Global using the current version at the time coding is first initiated and will be presented with counts and percentages by treatment for Anatomical Therapeutic Chemical (ATC) class and standardized drug name. Subjects will be counted at most once for a drug and class; this will be presented for the safety population. Concomitant medications will also be presented in a listing.

Prior medications include any medications recorded on the electronic case report form (eCRF) that were taken at any time prior to injection of study therapy. Prior medications will include medications that are ongoing at time of injection of study therapy. Prior medications will be presented in a manner parallel to the concomitant medications.

Additionally, prohibited and restricted medications will be summarized as above and presented in a listing. Restricted medications include medications for LDH taken at stable dose and regimen as described in protocol section 6.6.2. A separate summary for concomitant medication excluding those taken for LDH will also be provided.

Prior and concomitant therapies will be presented in a listing; prohibited therapies and block procedures will be flagged in this listing.

6.3 Medical History

All medical history for the safety population will be presented in a listing.

The number and percentage of subjects having received nerve block, epidural injection, and Facet block will be summarized for each treatment group.

7. EFFICACY EVALUATION

7.1 Overview of Efficacy Analysis Issues

7.1.1 Handling of Dropouts or Missing Data

For the efficacy analysis based on repeated-measures models of continuous endpoints, missing data will be implicitly handled via a mixed-effect model, without explicit imputation. Inferences based on this approach are unbiased under the assumption of missing at random (MAR), which is a weaker and more generally true assumption than missing completely at random (MCAR).

For the primary efficacy analysis, sensitivity analysis based on multiple imputation (MI) methods that changes imputation methods by missing pattern such as discontinuations due to AEs, lack of efficacy, and other will be performed for the mITT population.

For the analysis of percentages of positive responders by composite definition, no imputation will be performed. However, subjects will only be considered responders if they meet all criteria, thus, subjects with missing data and dropouts will implicitly be treated as non-responders.

No replacement of any missing data will be made for the safety analyses.

Additionally, see Section [7.3.2.1](#) for data handling regarding the VAS pain scores for the definition of a non-missing week and data censoring rules.

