11.8.4 Missing Data

For the efficacy analyses based on repeated-measures models of continuous endpoints, missing data will be implicitly handled via a mixed-effect model, without explicit imputation. Inferences based on this approach are unbiased under the assumption of missing at random, which is a weaker and more generally true assumption than missing completely at random. For the primary efficacy analysis, sensitivity analysis based on multiple imputation methods that changes imputation methods by missing pattern such as discontinuations due to AEs, lack of efficacy, and other will be performed for the mITT population.

For the analysis of percentages of positive responders by composite definition, subjects who discontinue the study because of AEs related to LDH or lack of efficacy and subsequently have missing efficacy data will be classified as non-responders.

No replacement of any missing data will be made for the safety analyses.

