11.8.6 Sample Size Determination

It is planned to enroll approximately 320 subjects, 160 in the SI-6603 group and 160 in the control group.

Sample size estimation is based on using the mean difference in the worst leg pain score change from baseline in the primary efficacy analysis. The following assumptions were made to compute the sample size:

- The 2-sample t-test comparing the group means of the change from baseline was used. (The 2-sample t-test approximates the test of the null hypothesis based on the repeated measures model that will be used in the primary efficacy analysis.)
- Treatment difference between SI-6603 and control groups of 12 mm
- Common standard deviation (SD) of 30 mm
- Dropout rate of 15%
- Power of 90%
- Two-sided significance level of 5%

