7.3.2.2 Sensitivity analyses

As a sensitivity analysis, missing data for participants in the mITT population will be imputed via MI. Twenty repeats of the imputation will be performed using Markov Chain Monte Carlo (MCMC) assuming non-monotone missing. Where the subject was discontinued due to lack of efficacy, due to an AE (with the exception of COVID-19), the subject has met the criteria for treatment failure as described in Section 7.3.3.4, or the subject's values are censored due to a prohibited therapy as described in Section 7.3.2.1, missing values will be imputed drawing from the baseline values, conditioned on the non-missing post-baseline values, of all participants in the mITT population under the assumption that they are missing not at random (MNAR); duration of leg pain will be included as a covariate.

If the study medication was discontinued for any other reason, values will be imputed within treatment group using MI under the assumption that they are missing at random (MAR) with covariates for duration of leg pain, and the weekly average worst leg pain score recorded at each time point (including baseline). The MAR approach will also be applied for sporadic missing values (prior to discontinuation). Values missing due to COVID-19, whether the result of early termination or sporadic missing values, are assumed MAR and unrelated to the endpoint of the weekly average VAS worst leg pain.

Data will be imputed for the full set of visits as described above and the same output will be used as a sensitivity for both the primary at Week 13 and the secondary endpoint at Week 52.

The MMRM analysis as described for the primary will be repeated for each of the 20 sets of data and combined using SAS PROC MIANALYZE. See Appendix [13.2](#) for the list of random seeds.

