7.3.3.3 Other Secondary

All endpoints, including the primary and key secondary endpoints, will be summarized by treatment group and by time point. The differences of other secondary endpoints between the SI-6603 and control groups will be analyzed at each time point they are collected as below.

- A similar longitudinal analysis model will be used as described in the primary efficacy analysis for the analysis of change from baseline in pain intensity scores, function scores, QOL scores, and volumes (intervertebral disc and herniation), by including the corresponding baseline value as the fixed effect instead of the baseline worst leg pain score.
- Percentage change from baseline in intervertebral disc and herniation volumes will be summarized in a line graph with error bars.
- Neurologic status as determined by neurological examinations will be compared between treatments with a difference in proportions Z test. In the case of low counts (<5 expected in a cell), a Fisher's exact test will be used. Outcomes will include SLR test, sensation, muscle strength, and deep tendon reflex. Counts and percentages in each category will be presented along with 95% confidence intervals, the difference in the percentages and its 95% Wald CI. Percentages will be reported out of non-missing values.
- For the global assessments of PGIC score and CGIC score, responder analysis with the two best categories as "responder" will be compared between treatments with a difference in proportions Z test. In the case of low counts (<5 expected in a cell), a Fisher's exact test will be used. Counts and percentages in each category for the PGIC and CGIC will be presented as well as the responder/non-responder counts and percentages along with 95% confidence intervals, the difference in the percentages of responders and its 95% Wald CI. Subjects with missing values will be considered non-responders.
- Scores on the WPAI will be analyzed with the analysis of covariance model including the baseline value and duration of leg pain as covariates.
- The incidence of rescue medication use will be compared between treatments with a difference in proportions Z test. In the case of low counts (<5 expected in a cell), a Fisher's exact test will be used. The amount of rescue medication use will be analyzed with the Wilcoxon rank sum test.

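### Straight-leg-raise and neurologic percentages drop withdrawn failures that the other responder endpoints count, and the SAP's wider missing-data rule for the composite is not declared

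*SAP*

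**What the plan says.** **Neurologic endpoints.** SAP 7.3.3.3 compares SLR, sensation, muscle strength and deep tendon reflex between arms as proportions and adds: "Percentages will be reported out of non-missing values". This follows the general convention in SAP section 3, which uses subjects with non-missing data as the denominator of every percentage.

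**Other responder endpoints.** In the same section, subjects with missing values are non-responders for PGIC and CGIC and for the 30% and 50% leg-pain thresholds. For the composite responder, SAP 7.1.1 says that no imputation is done but that "subjects with missing data and dropouts will implicitly be treated as non-responders".

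**Protocol.** For the composite, Protocol 11.8.4 classifies as non-responders "subjects who discontinue the study because of AEs related to LDH or lack of efficacy and subsequently have missing efficacy data". It gives no rule for other missing data.

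**Declared changes.** SAP section 11 lists three: imputation after a prohibited procedure, the multiplicity algorithm, and recurrence of LDH. The composite rule is not among them.

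**COVID-19.** SAP 5.1 notes that "individual assessments may have been omitted due to COVID-19". In the multiple-imputation sensitivity analysis, SAP 7.3.2.2 says: "Values missing due to COVID-19, whether the result of early termination or sporadic missing values, are assumed MAR and unrelated to the endpoint". That sentence goes on to name weekly average worst leg pain as the endpoint meant.

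**The concern.** The reasons for leaving this trial are partly outcomes. Protocol 5.1 and 6.7.1 withdraw subjects who have lumbar surgery for LDH, or a block procedure before Week 13, and allow withdrawal for poor response. Under SAP 7.1.2 a discontinuation examination is used only at a scheduled visit whose window contains it. At later visits the subject is missing. A subject who leaves on day 60, for example, falls between the Week 6 window (days 36 to 50) and the Week 13 window (days 85 to 106). That examination is listed but not summarized.

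Inclusion criterion 3c requires a positive SLR at entry. A subject who leaves for lack of efficacy or has surgery has no documented conversion at the missed visit and belongs more naturally with the failures. Dropping such subjects raises the percentage negative, most of all in the arm with more of them. The same person is then a failure for PGIC, the pain thresholds and the composite but absent from the SLR table, so these results cannot be read side by side.

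The composite has a different problem. Its rule is wider than the protocol's, is not declared, and does not fit the section 3 denominator unless it is stated as an exception.

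**Working it through.** **The plan's own figure.** The sample size rests on "Treatment difference between SI-6603 and control groups of 12 mm" and "Common standard deviation (SD) of 30 mm", two-sided 5%, power 90% and 15% dropout.

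- n per arm = 2 × (1.960 + 1.282)² × 30² / 12² = 131.3, so 132.
- 132 / 0.85 = 155.3, so 156 per arm and 312 in total.
- The exact t-test gives 133, then 157 per arm and 314 in total.

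Both agree with the planned 320. Nothing below alters that number. The documents state no response rate or power for the binary endpoints, so all rates below are assumptions.

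**SLR.** Assume 60% (SI-6603) v 45% (control) of all subjects are SLR-negative. A share w in each arm leaves for failure while still positive, and nothing else is missing. The reported rate is p / (1 − w).

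| w, SI-6603 / control | Reported rates | Difference (true 15.0) |
|---|---|---|
| 5% / 12% | 0.60/0.95 = 63.2%; 0.45/0.88 = 51.1% | 12.0 |
| 8.5% / 8.5% | 0.60/0.915 = 65.6%; 0.45/0.915 = 49.2% | 16.4 |
| 12% / 5% | 0.60/0.88 = 68.2%; 0.45/0.95 = 47.4% | 20.8 |

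Counting these subjects as not negative returns 60% v 45% in every row.

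**Composite.** Assume 45% v 30% response among subjects with data and a missing share d unrelated to response. A fraction f of the missing cases is due to the protocol's reasons.

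- SAP rule: p × (1 − d).
- Reason-based rule: p × (1 − d) / (1 − d × (1 − f)), with other missing subjects leaving the denominator. The protocol does not say this; it is my simplification of treating them as missing at random.

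| d, SI-6603 / control | SAP rule | Difference, SAP | Difference, reason-based: f = 0 / 0.5 / 1 |
|---|---|---|---|
| 15% / 15% | 38.25% v 25.5% | 12.75 | 15.0 / 13.8 / 12.75 |
| 10% / 20% | 40.5% v 24.0% | 16.5 | 15.0 / 16.0 / 16.5 |
| 20% / 10% | 36.0% v 27.0% | 9.0 | 15.0 / 11.6 / 9.0 |

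With no effect (40% v 40%) and 10% / 20% missing, the SAP rule shows 36.0% v 32.0%, a 4.0-point difference produced by missingness alone. In these scenarios the two rules agree when every missing case has a protocol reason (f = 1).

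**The case against.** The neurologic denominator is the SAP's stated default, applied as written, and not a slip. For the composite, the protocol defines a responder as someone who meets all four criteria and leaves analysis detail to the SAP. Counting an incomplete subject as a non-responder follows from that definition and is a common choice. Some routes to missingness are also narrowed. Leg pain comes from a daily diary, and SAP 7.3.2.1 searches for alternative intervals. An in-window discontinuation visit is used. A subject who fails any observed criterion is a non-responder whatever else is missing. These endpoints are supportive, and SAP 7.3.4 says none outside the hierarchy will be considered statistically significant.

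All of this stands. It supports keeping the composite rule as the main analysis if the sponsor wishes, and it limits the weight of the point. It does not explain why withdrawal for failure counts against a subject on every responder scale except the neurologic ones, or why the wider composite rule is missing from section 11.

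A reader might infer more than the documents support:

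- **That the SAP contradicts its own COVID-19 assumption.** The missing-at-random statement belongs to the imputation sensitivity analysis of leg pain, extended to the key secondary endpoints by SAP 7.3.3.2. The composite is neither. Leg pain and ODI are components of it, so there is a difference of principle but no direct conflict.
- **That the SAP overrides a protocol rule limiting failure to two reasons.** Protocol 11.8.4 names those reasons and is silent on the rest. The four criteria are the same in both documents, so the composite itself has not been replaced.
- **That a missing X-ray makes a subject a composite failure.** Treatment failure is recorded by the investigator as yes or no, and the documents do not say how a missing X-ray affects it.

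**Conclusion.** The point holds in two limited parts.

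First, the SLR denominator removes subjects whose withdrawal is itself evidence of failure. Under the assumed rates the reported difference is 12.0 points instead of 15 when control loses more of them, and above 15 when losses are equal or heavier on SI-6603. The direction is not known in advance. The figures assume that those who leave for failure are still SLR-positive and that nothing else is missing. For sensation, strength and reflex the argument is weaker, because the protocol's definition of radiculopathy makes such deficits possible but not required. Some subjects have nothing to recover.

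Second, the composite rule extends beyond the reasons the protocol names, is undeclared, and needs to be stated as an exception to SAP section 3. It might be taken as reliably conservative, but attenuation toward zero is assured only when missingness is equal between arms. Unequal missingness gives 9.0 to 16.5 points around an assumed 15.

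No confirmatory conclusion, the primary analysis or the sample size is affected.

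**What to change.** 1. **SLR.** Count a subject missing after discontinuation for lack of efficacy or an LDH-related adverse event (the Protocol 11.8.4 reasons), or after lumbar surgery, as not negative.
2. **Sensation, strength, reflex.** Do the same as a sensitivity analysis, or carry forward the baseline status.
3. **Composite.** All-missing-as-non-response may stay as the main analysis. List it in SAP section 11, and state its denominator as an exception to section 3.
4. **Composite sensitivity analysis.** Count only the protocol's reasons as failure, and treat other missing values, including COVID-19 omissions, as missing at random. Leg pain and ODI imputations are already planned under SAP 7.3.2.2 and 7.3.3.2. Neurologic status and treatment failure would need a further step.

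The data for item 1 are already collected: reason for discontinuation, adverse events leading to discontinuation, and surgery dates to Week 52 even for withdrawn subjects. SAP 5.1 records only one primary reason and does not separate LDH-related adverse events, so that classification should be fixed before unblinding. The cost is SAP wording and a small amount of programming. Neurologic rates will look slightly less favourable.
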